### **8.2.3 Shift Table for Investigator's Global Assessment Scores up to Week 4**

Based on the OC and LOCF data sets, a shift table will be created for IGA scores (0, 1, 2, 3, and 4) at Weeks 1, 2, and 4.

### **8.2.4 Change From Baseline Through Week 4 in the Total EASI Score and Each EASI Clinical Sign Score**

Based on the OC and LOCF data sets, the analysis will be performed in the same manner as for the change from baseline in IGA scores. In addition to clinical signs (erythema, infiltration/papule, excoriation, and lichenification), scores on body regions (face, neck, and head; upper limbs; trunk; and lower limbs) will also be analyzed in the same manner. For EASI, the percentage change will also be analyzed. A graph will be created for the least square mean and standard deviation for the change from baseline in the total EASI score calculated by MMRM for each treatment group.

### **8.2.5 Change From Baseline Through Day 8 in VRS for Pruritus**

Based on the OC data set, the analysis will be performed in the same manner as for the change from baseline in IGA scores. Timepoints will include baseline through Day 8.

### **8.2.6 Change From Baseline Through Week 4 in VRS for Pruritus**

Based on the OC and LOCF data sets, the analysis will be performed in the same manner as for the change from baseline in IGA scores. Timepoints will include baseline, Weeks 1, 2, and 4.

### **8.2.7 Change From Baseline Through Week 4 in the Total POEM Score**

Based on the OC and LOCF data sets, the analysis will be performed in the same manner as for the change from baseline in IGA scores. The percentage change in the total POEM score will also be analyzed in the same manner.

### **8.2.8 Change From Baseline Through Week 4 in the Total Affected BSA (%)**

Based on the OC and LOCF data sets, the analysis will be performed in the same manner as for the change from baseline in IGA scores.

## **8.3 Subgroup Analyses**

The success rate in IGA (IGA of 0 or 1 with improvement of at least 2 grades) and EASI 75 will be analyzed for each of the following subgroups in the same manner as the primary endpoint in [Section 8.1.1](#).

Age: 2 to 6 years old, 7 years and older

Sex: male, female

IGA score at baseline: 2 (mild), 3 (moderate)

Severity of AD: mild, moderate, severe, very severe

Total EASI score at baseline: less than 15, 15 and above

Affected BSA at baseline: less than 20%, 20% and above

## **8.4 Exploratory Analysis of Age Factor**

Logistic regression analysis will be performed using treatment group as the main effect, baseline IGA (2 or 3) and age as covariates, and success rate in IGA (IGA of 0 or 1 with improvement of at least 2 grades) at Week 4 as a response variable. An adjusted odds ratio along with its 95% confidence interval and p value will be determined. For the age

factor, in addition to age categories of “2 to 6 years old” and “7 to 14 years old,” data will be exploratorily analyzed as a continuous value or, if necessary, in other age categories. The SAS code is given below.

```
proc logistic ;  
  class Treatment(param=ref ref= "Placebo") Agegroup BaselineIGA;  
  model Response(event="有効") = Treatment Agegroup BaselineIGA /clodds=wald  
  orpvalue;  
run;
```

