As described above, efficacy of the 0.3% and 1% OPA-15406 ointment groups surpassed that of the vehicle group in pediatric AD patients in the Japanese phase 2 trial results, and significant difference was observed in the efficacy of the 1% OPA-15406 ointment group against the vehicle group in adult AD patients in the Japanese phase 2 trial results. The number of patients in the phase 2 pediatric AD trial in Japan is approximately one third of that in the phase 2 adult AD trial. Thus, it was considered that the recommended dose should be established after evaluating the efficacy of 0.3% and 1% OPA-15406 ointment in pediatric AD patients in a large-scale trial and considering the risk-benefit profile not only in the overall group but also by ages. Therefore, it was judged ethically and scientifically appropriate to conduct this trial to demonstrate the superiority of 0.3% and 1% OPA-15406 ointment to the vehicle in pediatric AD patients when administered the 0.3% or 1% OPA-15406 ointment twice-daily for 4 weeks.

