### 8.1.1 Primary Efficacy Analysis

The efficacy of the 0.3% and 1% OPA-15406 groups will be demonstrated compared to the vehicle group based on the primary endpoint, the success rate in IGA at Week 4. Overall type I errors will be controlled using a closed testing procedure. First, the 1% OPA-15406 treatment group and the vehicle group will be compared. If significant at the two-sided significance level of 5%, the 0.3% OPA-15406 treatment group and the vehicle group will then be compared at the two-sided significance level of 5%. The Cochran-Mantel-Haenszel test will be conducted for comparison using the baseline IGA (2 or 3) and age (“2 to 6 years” or “7 to 14 years”) as a stratification factor. The difference in the success rate in IGA and its two-sided 95% confidence interval (common risk difference adjusted by Mantel Haenszel method and its two-sided 95% confidence interval) between the vehicle group and 0.3% or the 1% OPA-15406 group will be determined. Also, the two-sided 95% confidence interval of the success rate in IGA in each treatment group (based on Clopper-Pearson method) will be calculated. In addition, the success rate in IGA in each treatment group at Week 4 and its two-sided 95% confidence interval will be plotted and the dose-response relationship will be graphically assessed.

The SAS code for the Cochran-Mantel-Haenszel test and to determine the difference in the success rate and two-sided 95% confidence interval is as follows:

```
proc freq ;
  tables Agegroup*BaselineIGA*Treatment*Response / riskdiff(common) cmh ;
run;
```

A supplementary analysis will be performed using data which includes missing data imputed by Last Observation Carried Forward (LOCF) and Observed Cases (OC) data which does not include the imputed missing data in the same manner.

Data at Weeks 1 and 2 will also be analyzed in the same manner as the primary endpoint at Week 4.

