### 9.2 Adverse Events

All AEs will be coded by System Organ Class (SOC) and Preferred Term (PT) using the MedDRA.

For the following treatment-emergent adverse events (TEAEs) occurring after the start of IMP administration, the number and percentage of subjects will be calculated by treatment group and for all subjects. Skin and subcutaneous tissue disorders will be summarized in the same manner by grade as specified in the Common Terminology Criteria for Adverse Events (CTCAE) version 4.0 translated into Japanese by JCOG.

- TEAEs
- TEAEs resulting in death
- Serious TEAEs
- TEAEs leading to discontinuation of IMP administration
- TEAEs by severity
- TEAEs (skin and subcutaneous tissue disorders alone) by CTCAE grade
- TEAEs in treatment areas

Also, for the TEAEs and non-serious TEAEs occurring in at least 5% of subjects in each treatment group, the number and percentage of subjects will be calculated for each treatment group.

Adverse reactions (TEAEs for which a causal relationship with the IMP cannot be ruled out) will be analyzed in the same manner as TEAEs.

If the same event occurs more than once in the same subject, the most severe will be used.

The above data will also be presented by age category (2 to 6 years old and 7 years and older).

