- CT-6.1.6 Subgroup Analysis of Responder Rate for Overall IGA Score - by Affected Body Surface Area (<20%, 20%=<)
- CT-6.2.1 Subgroup Analysis of 75% Over Responder Rate for Overall EASI Score - by Age
- CT-6.2.2 Subgroup Analysis of 75% Over Responder Rate for Overall EASI Score - by Sex
- CT-6.2.3 Subgroup Analysis of 75% Over Responder Rate for Overall EASI Score - by IGA Score at Baseline
- CT-6.2.4 Subgroup Analysis of 75% Over Responder Rate for Overall EASI Score - by Severity of Atopic Dermatitis
- CT-6.2.5 Subgroup Analysis of 75% Over Responder Rate for Overall EASI Score - by Total EASI Score at Baseline (<15, 15=<)
- CT-6.2.6 Subgroup Analysis of 75% Over Responder Rate for Overall EASI Score - by Affected Body Surface Area (<20%, 20%=<)
- CT-6.3.1 Exploratory Analysis of Impact of Age Factor to efficacy by Logistic Analysis -by Age (Continual)
- CT-6.3.2 Exploratory Analysis of Impact of Age Factor to efficacy by Logistic Analysis -by Age (2-6 Years, 7-14 Years)
- CT-7.1.1 Summary of Treatment Compliance

- CT-7.1.2 Summary of Treatment Compliance for Number of Administrations
- CT-7.2.1 Extent of Exposure to Trial Medication
- CT-7.2.2 Summary of Exposure
- CT-8.1.1 Adverse Events (All Causalities)
- CT-8.1.2 Adverse Events According to Application Site (All Causalities)
- CT-8.2.1.1 Incidence of Treatment-emergent Adverse Events by System Organ Class
- CT-8.2.1.2 Incidence of Treatment-emergent Adverse Events by System Organ Class
- CT-8.2.1.3 Incidence of Treatment-emergent Adverse Events by System Organ Class
- CT-8.2.2.1 Incidence of Treatment-emergent Adverse Events by System Organ Class and Preferred Term
- CT-8.2.2.2 Incidence of Treatment-emergent Adverse Events by System Organ Class and Preferred Term
- CT-8.2.2.3 Incidence of Treatment-emergent Adverse Events by System Organ Class and Preferred Term
- CT-8.2.3.1 Incidence of Treatment-emergent Adverse Events by System Organ Class, Preferred Term and Severity
- CT-8.2.3.2 Incidence of Treatment-emergent Adverse Events by System Organ Class, Preferred Term and Severity
- CT-8.2.3.3 Incidence of Treatment-emergent Adverse Events by System Organ Class, Preferred Term and Severity
- CT-8.2.4.1 Incidence of Treatment-emergent Adverse Events by System Organ Class, Preferred Term and CTCAE Grade
- CT-8.2.4.2 Incidence of Treatment-emergent Adverse Events by System Organ Class, Preferred Term and CTCAE Grade

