- CT-10.1.1 Mean Change From Baseline in Laboratory Test Values: Serum Chemistry
- CT-10.1.2 Mean Change From Baseline in Laboratory Test Values: Hematology
- CT-10.2.1 Shift Tables of Clinical Laboratory Test Results: Serum Chemistry
- CT-10.2.2 Shift Tables of Clinical Laboratory Test Results: Hematology
- CT-10.2.3 Shift Tables of Clinical Laboratory Test Results: Urinalysis
- CT-11.1 Mean Change From Baseline in Vital Sign Parameters
- CT-11.2 Listing of Vital Signs Abnormalities

- CT-11.3 Incidence of Potential Clinical Significance in Vital Signs
- CT-11.4 Criteria for Vital Signs Potential Clinical Significance
  
- CF-1.0 Responder Rate for Overall IGA Score by Visit
- CF-1.1 Incidence of Responder Rate for Overall IGA Score by Visit
- CF-1.2 Incidence of 75% Over Responder Rate for Overall EASI Score by Visit
- CF-1.3 Incidence of 90% Over Responder Rate for Overall EASI Score by Visit
- CF-1.4 Incidence of 50% Over Responder Rate for Overall EASI Score by Visit
- CF-1.5 Incidence of Responder Rate for Overall IGA Score by Visit - Less Than 7 Years
- CF-1.6 Incidence of Responder Rate for Overall IGA Score by Visit - Greater Than or Equal to 7 Years
- CF-2.1 Least Square Means of Change from Baseline in Overall IGA Score by Visit - MMRM
- CF-2.2 Least Square Means of Change from Baseline in Overall EASI Score by Visit - MMRM

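### Cheap improvement: the exploratory age model gives one odds ratio per dose for all ages, and no planned output compares the treatment effect between ages

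*SAP*

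**What the plan says.** SAP 8.4 describes the age analysis as "Logistic regression analysis will be performed using treatment group as the main effect, baseline IGA (2 or 3) and age as covariates", with Week 4 IGA success as the response. The right-hand side of the code is "Treatment Agegroup BaselineIGA /clodds=wald", with no product term. Age enters as two categories, as a continuous value or, if needed, in other categories. Protocol 7.4.4 describes the same model. The listed outputs are CT-6.3.1 (continuous age) and CT-6.3.2 (two categories).

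SAP 8.3 analyses IGA success and EASI 75 within subgroups, including "Age: 2 to 6 years old, 7 years and older", by the method of the primary analysis. Each age group therefore gets its own "common risk difference adjusted by Mantel Haenszel method and its two-sided 95% confidence interval" (CT-6.1.1 and CT-6.2.1). Responder figures by age are listed as CF-1.5 and CF-1.6, and SAP 9.2 tabulates adverse events by age category.

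On why age matters, Protocol 2.1 wants the recommended dose set after "considering the risk-benefit profile not only in the overall group but also by ages". Protocol 7.1 and SAP 4 find 72 per group sufficient for 90% power and then set 80, citing an exploratory look at age categories.

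**The concern.** A model with treatment, age and baseline IGA as main effects estimates two things: how age relates to success overall, and one treatment odds ratio per dose. That odds ratio is the same at every age by construction, whether age is categorical or continuous. The question raised in Protocol 2.1, whether benefit differs by age, is a question about treatment by age. The model cannot answer it.

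The subgroup tables come closer, but they put two age-specific effects side by side without a comparison. A reader may then judge the gap by whether each interval excludes zero, which is not a comparison of the two effects. What is at stake is the interpretation of the age results when a dose is recommended. The primary conclusion is not involved.

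**Working it through.** **1. Base inputs.** Planning rates are 36% (1% ointment) and 12% (vehicle), two-sided 5%, 90% power, 72 per group (SAP 4). The continuity-corrected formula for two proportions gives 72.5, rounded up to 73. The exact power of Fisher's test at 72 per group is 90.7%. The stated 72 is reproduced, and nothing below disputes it.

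**2. Size per age group.** The plan has 80 per group and a 1:1 age target (SAP 3.3), so about 40 per arm per age group. The documents give no success rates by age. I assume the planning rates in both age groups unless stated.

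**3. Within one age group** (unadjusted):
- SE of the risk difference = √(0.36×0.64/40 + 0.12×0.88/40) = √0.0084 = 0.0917. The 95% half-width is 1.96×0.0917 = 18.0 points.
- Power is about 72%. With identical true effects, the chance that exactly one of the two age groups is significant is 2×0.72×0.28 ≈ 40%.

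**4. The missing contrast** (one age group's risk difference minus the other's). The groups are disjoint, so variances add:
- SE = √(2×0.0084) = 0.1296. The half-width is 1.96×0.1296 = 25.4 points.
- With Mantel-Haenszel adjustment for baseline IGA (Sato variance; assumed share with IGA 3 of 50–85%; odds of success 1 to 5 times higher for IGA 3), the half-width is 24.4 to 25.4 points at 36%/12%. At 40%/8.3% it is 23.9 to 24.7, and at 37.5%/8.3% it is 23.7 to 24.4.
- At 72 per group (36 per arm per age group) the unadjusted half-width would be 1.96×√(2×0.336/36) = 26.8 points, so moving to 80 gains about 1.4 points.
- Power for 42% and 30% against 12% (a 12-point gap): SE 0.1289, 0.12/0.1289 = 0.93, power about 15%. A gap of about 36 points is needed for 80% power.

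**5. Odds-ratio scale.** SE of one log odds ratio = √(1/14.4 + 1/25.6 + 1/4.8 + 1/35.2) = 0.588. SE of the log ratio of odds ratios = 0.588×√2 = 0.831. The 95% CI is the estimate divided or multiplied by exp(1.96×0.831) = 5.1. For continuous age (assumed uniform over whole years within each category) the SE of the treatment-by-age term is 0.110 per year, a CI factor of about 2.9 over five years.

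**6. What the planned outputs would show.** These rates are assumed for illustration: active 48% in one age group and 24% in the other, vehicle 12% in both, 40 per cell, no baseline IGA.

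| Output | Result (95% CI) |
|---|---|
| 8.4 main-effects odds ratio (true values 6.8 and 2.3) | 4.3 (1.9 to 9.7) |
| 8.3-type risk differences | 36 points (17.5 to 54.5); 12 points (−4.6 to 28.6) |
| Contrast, not planned | 24 points (−0.9 to 48.9) |
| Ratio of odds ratios, not planned | 0.34 (0.07 to 1.79) |

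One subgroup interval excludes zero and the other does not, yet the contrast includes zero. That is the misreading the added row would prevent.

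**7. The scales can disagree.** Take a constant odds ratio of 4.125 (36% vs 12%) with vehicle at 8% in one age group and 16% in the other. The risk differences are about 18 and 28 points: a gap of about 10 points, with a ratio of odds ratios of exactly 1.

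**8. Sparse cells.** The chance that at least one vehicle age group has no responder is 1 − (1 − (1−p)^40)²: 1.2% at p = 12% and 6.1% at p = 8.3% (the Phase 2 vehicle rate).

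**The case against.** The strongest reply is that nothing is broken. Protocol and SAP describe the same model, the code matches the text, and the table titles match the model. The stated purposes are largely served: efficacy, adverse events, disposition, demographics and baseline disease are all presented by age. Anyone can compute the between-age contrast from the 8.3 output. The contrast is also imprecise, since its half-width is about as large as the whole planned effect of 24 points, and an interval that usually includes zero may be misread as proof of a uniform effect. The expected misreading of the subgroup intervals is a prediction, and the illustrative rates come from no document.

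Much of this stands. It is why the point is an improvement only, why the additions are limited to one table and one supporting fit, and why a warning about intervals that include zero belongs with them. It does not remove the gap. The categorical contrast is derivable but not planned, and a treatment effect across continuous age needs a new fit. The homogeneity test that the primary code's `cmh` option can print does not fill it either: it spans the four age-by-baseline-IGA strata, is not named as an output, and is not an age contrast.

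A reader might infer that the SAP fails a protocol commitment, or that the increase to 80 was meant to power an age comparison. The documents support neither. No section promises an effect-modification analysis, and the increase is justified only by an exploratory look at age categories, with no target difference.

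**Conclusion.** This is a cheap improvement, not an error. The 8.4 model cannot show whether either dose works differently by age, and the age-specific effects in 8.3 are never compared, although the trial's own rationale gives age weight. It would be wrong to infer that effects by age go unexamined or that the primary result is affected. SAP 8.3 gives the age-specific estimates, and the primary test, alpha and sample size do not change.

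The gain is modest: an interval of about ±24 to 25 points for the between-age contrast, and about 15% power for a 12-point gap. These figures rest on 40 per arm per age group, equal rates in the two age groups for the interval width, and the assumed baseline IGA mix. The absence of the contrast and the interaction term rests on the text alone.

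**What to change.** 1. In CT-6.1.1 (Week 4 IGA success by age), add for each dose the difference between the two age-specific Mantel-Haenszel risk differences with its 95% CI. The SE is the square root of the sum of the squared subgroup SEs.
2. As a supporting exploratory result, refit the 8.4 model with a Treatment*Age term, once for the two age categories and once for continuous age. Report the interaction estimate with its 95% CI. Use reference coding for Agegroup, since the planned code sets it only for Treatment; the categorical interaction coefficient is then the log ratio of odds ratios (under +1/−1 coding it would be half of that). Keep the main-effects model as the overall adjusted estimate.
3. If a sparse-data method is wanted, name one in advance, for example Firth with profile-likelihood intervals, and use it in every case rather than switching when a cell is empty.
4. Label the results exploratory estimates. State that an interval including zero does not show a uniform effect by age, and that the risk-difference and odds-ratio scales can disagree.

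The cost is one row per dose in an existing table, two refits with one extra table, and a short interpretive note. The downside is low precision, which the intervals will make plain.

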## 9 Safety Analyses

The following analyses will be performed in the SS.

### 9.1 Extent of Exposure

Based on the SS, the descriptive statistics will be presented for the total amount and the amount per dose of the IMP by treatment group and in total. Also, descriptive statistics will be presented in the same manner by taking into consideration the concentration of the IMP (0.3% OPA-15406, 1% OPA-15406, and vehicle [0%]). Where the weight of IMP at retrieval is unknown, the amount of administration will be calculated by assuming that the retrieved weight is 0.

### 9.2 Adverse Events

All AEs will be coded by System Organ Class (SOC) and Preferred Term (PT) using the MedDRA.

For the following treatment-emergent adverse events (TEAEs) occurring after the start of IMP administration, the number and percentage of subjects will be calculated by treatment group and for all subjects. Skin and subcutaneous tissue disorders will be summarized in the same manner by grade as specified in the Common Terminology Criteria for Adverse Events (CTCAE) version 4.0 translated into Japanese by JCOG.

- TEAEs
- TEAEs resulting in death
- Serious TEAEs
- TEAEs leading to discontinuation of IMP administration
- TEAEs by severity
- TEAEs (skin and subcutaneous tissue disorders alone) by CTCAE grade
- TEAEs in treatment areas

Also, for the TEAEs and non-serious TEAEs occurring in at least 5% of subjects in each treatment group, the number and percentage of subjects will be calculated for each treatment group.

Adverse reactions (TEAEs for which a causal relationship with the IMP cannot be ruled out) will be analyzed in the same manner as TEAEs.

If the same event occurs more than once in the same subject, the most severe will be used.

The above data will also be presented by age category (2 to 6 years old and 7 years and older).

### **9.3 Clinical Laboratory Tests**

For each parameter (except qualitative urinalysis), the descriptive statistics will be calculated for measured values and changes from the baseline at each timepoint by treatment group. For qualitative urinalysis values of clinical laboratory tests, a shift table at each timepoint against the baseline will be created for each treatment group. For clinical laboratory tests except qualitative urinalysis, a shift table for values before and after administration categorized as normal, high, or low relative to the reference value will be created for each treatment group.

### **9.4 Vital Signs and Body Weight**

For body weight, body temperature, blood pressure (systolic and diastolic), and pulse rate, the descriptive statistics will be calculated for measured values and changes from baseline at each timepoint by treatment group. The number and percentage of subjects with clinically abnormal changes (Appendix 1) in body temperature, blood pressure (systolic and diastolic), and pulse rate will be calculated by treatment group and for all subjects. For clinically abnormal changes, all data after starting administration, except for baseline or missing timepoints, will be included in the evaluation. Also, a list of subjects with clinically abnormal changes will be created.

### **9.5 Physical Examination**

Not applicable.

### **9.6 Electrocardiogram**

Not applicable.

## **9.7 Liver Function Tests**

The number and percentage of subjects with abnormal changes in liver function (Appendix 2) will be calculated by treatment group. Also, a list of abnormal changes in liver function will be created. For clinically abnormal changes, all data after starting administration, except for baseline or missing timepoints, will be included in the evaluation.

